2.2 Overview of Proposed Study

This is a prospective, randomized, mixed methods, comparative effectiveness trial (1:1 randomization) of perioperative telemonitoring in cancer surgery (GI, GU, GYN). This study will be conducted in compliance with the protocol, Good Clinical Practice (GCP) and the applicable regulatory requirements.

2.3 Preclinical Studies

Not Applicable

2.4 Human Studies

The remote perioperative care model is based on evidence from our previous work and several other telemonitoring interventions, including Basch and colleagues' electronic symptom assessment trial⁹, and Peterson and colleagues' CYCORE trial on mobile and sensor technology in head and neck cancer.⁶⁹ Our previous research in major abdominal cancer surgery shows that the median number of steps before surgery was 6,562; this number decreased to 483 during hospitalization, and increased to only 2,483 in the first 2 weeks post-discharge (**Figure 1**). We observed a correlation between daily steps and risk for postoperative complications as measured by the Comprehensive Complications Index (CCI) (**Figure 2**). The median number of steps at

day 7 was 1,689 (19% of steps at baseline). This strongly correlated with CCI score ($r=-0.64$, $p<0.05$), where patients with fewer daily steps were at higher risk for postop complications. Adherence rate for wearing the pedometer device was 88%. Individual symptom scores for pain, fatigue, sleep, and appetite had the highest severity during week 1 post-discharge.

[figure not shown]

Figure 1. Median daily steps measured before surgery (pre-op), during hospitalization, and recovery (post-discharge)

[figure not shown]

Figure 2. Association between CCI and daily steps at post-op day 7

Of the 160 monitoring encounters, 34% generated an alert. Most of the alerts were generated during the first week post-discharge. 72% of the telephone encounters triggered by an alert were for symptom management. The most commonly reported issue during the encounters was for pain. For acceptability, patients reported that the telemonitoring program was easy to use. Patients reported no difficulty in answering PROs, and the majority found that the length of time was just right for completing ePROs (95%) and using the pedometer (70%). About 25% of patients thought that the length of time for pedometer monitoring was too short (up to 2-4 weeks after discharge), and desired to use the program longer.¹⁵

3.0 Patient Eligibility

3.1 Inclusion Criteria

The study sample will consist of 398 patients (199 per group) across the enrollment sites. We will also enroll about 40 patients for 4 focus groups; this will yield a final total of 438 participants overall. This sample size takes into account an anticipated 20% attrition. The attrition rate is based on our pilot and previous studies in GI and thoracic surgery. We expect to have complete evaluable data on 332 patients (166 per group) at 30 days post-discharge; the 332 evaluable patients will provide sufficient power for the primary endpoints. Patient eligibility criteria include: 1) cancer patients scheduled to undergo major abdominal surgery for GI, GU, or GYN malignancies or presumed GI, GU, or GYN malignancies (as determined by surgeons); 2) age 18 years and older, and 3) ability to read and understand English or Spanish.

Several approaches will be undertaken to maximize ethnic minority recruitment and retention. These include: 1) using bilingual (English and Spanish) team members; and 2) weekly team meetings to assess ethnic minority accrual status at all four participating sites. In addition, we will leverage expertise from City of Hope's Center of Community Alliance for Research & Education (CCARE) and Division of Health Equities to develop 1) appropriate standard operating procedures (SOPs) on ethnic minority recruitment, and 2) appropriate recruitment materials (IRB approved brochures, flyers).

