13.2 Statistical Analysis Plan

Data Management - We expect a total of 12 symptom evaluations per participant over the 3-4 month study duration. With a total sample of 332, this yields approximately 4,000 data collection encounters overall. We expect a large number of daily steps data observations per subject, as functional recovery data will be continuously recorded on a daily basis over the study duration.

Data will be transferred in real-time (within 2 minutes of participant completion) from TapCloud™ to a REDCap (Research Electronic Data Capture) study database. Daily step count will be continuously transferred to the study database in real-time. The database resides in secure COH research networks for research team access only. An assigned master's-level Statistical Research Associate (SRA) with paid effort on the project will be responsible for coordinating monthly data transfer, auditing, and data cleaning. In the process of data transfer and mergers, the study biostatistician ([name]), SRA, and TapCloud™ representative will audit and clean the data, apply formats in statistical software, and export data into REDCap database.

Handling Missing Data and Lost to Follow-Up - We will integrate the following strategies to prevent, detect, and remedy missing data in real time. First, participants will receive a total remuneration of \$50 for providing data. Second, research staff will provide telephone/email reminders before each of the scheduled data collection timepoints to maximize adherence. Regular contact will also be provided to remind participants to wear the accelerometer. Third, research staff will provide each participant with a simple study calendar with data collection dates. Fourth, if no data is completed by participants, research staff will contact the participant in real-time to engage and assess. The Statistical Methods section below describes how data missing not at random will be handled in the analyses.

Preliminary Analysis - Descriptive statistics will be used to summarize all variables. Characteristics of participants at baseline will be reported in tabular form using appropriate descriptive statistics. Prior to hypothesis testing, the relationship between demographic variables and primary outcome variables (daily step count, postop complications) will be examined. Significant relationships/correlations will guide the addition of demographic variables to the analysis.

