Heterogeneity of Treatment Effect - Exploratory use of interaction terms will assess whether significant effects of the study intervention differ by sex or by age (i.e., above vs below 70 years). If found to be present, any such heterogeneity of treatment effect, not having been hypothesized in advance, will be reported as a preliminary finding that awaits confirmation in future studies.

Internal/External Validity and Avoidance of Bias - To limit possible confounding of the primary results, analyses of the prespecified hypotheses will be adjusted for covariates (age, sex, physical fitness at pre-surgical baseline). To assess the representativeness of study participants, their demographic characteristics (sex, age) will be compared to those of eligible patients who are approached for consent but decline to participate in the study. Our digital engagement platform will initiate reminder systems to reduce loss to follow-up.

Statistical Methods by Study Aims - Characteristics considered as potential covariates in all analyses will be age, sex, surgical technique, residential setting, and physical fitness at preoperative baseline. Any covariate that improves the model's fit to the observed data will be retained in the final analysis.

The analyses for Aims 1-3 will be by intention to treat (ITT); the ITT population will include all subjects who have given informed consent, been randomized to intervention or control arm, and undergone the planned cancer surgery.

Aim 1 – Allowing for an anticipated 20% attrition in use of accelerometer by Day 14 across both trial arms, an initial sample size of 332 (randomized 1:1) will provide (per East 6.5 software)

80% power to detect the hypothesized 14% difference in slope due to study intervention, using a 1-sided, repeated measures-difference of slope test with alpha=0.025.

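### 398 enrolled, 20% attrition and 332 evaluable cannot all hold, and 332 is the number after attrition in Section 3.1 but the starting number in Section 13.2

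*Combined protocol and SAP*

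**What the plan says.** Section 3.1 (Inclusion Criteria) gives the enrolled number: "The study sample will consist of 398 patients (199 per group) across the enrollment sites". It adds "This sample size takes into account an anticipated 20% attrition" and gives the source of that rate: "The attrition rate is based on our pilot and previous studies in GI and thoracic surgery". It then gives the yield, "We expect to have complete evaluable data on 332 patients (166 per group) at 30 days post-discharge", and ties power to it: "the 332 evaluable patients will provide sufficient power for the primary endpoints". In this section 332 is what remains after attrition.

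Section 13.2 (Statistical Analysis Plan) uses the same number differently:

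- **Aim 1:** "Allowing for an anticipated 20% attrition in use of accelerometer by Day 14 across both trial arms, an initial sample size of 332" is given 80% power at one-sided alpha 0.025. Here 332 is the number before the 20% loss.
- **Aim 2:** 332 patients randomized 1:1 are given 88% power. No loss to follow-up is expected, because the CCI comes from the medical chart.
- **Aim 3:** 332 is described as the sample size of the trial, with at least 80% power.
- **Data management:** "With a total sample of 332, this yields approximately 4,000 data collection encounters overall", based on 12 symptom evaluations per participant.

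The ITT population in Section 13.2 is limited to consenting patients who have "been randomized to intervention or control arm, and undergone the planned cancer surgery". The plan does not say whether the 20% includes patients who never have that surgery.

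**The concern.** There are two faults. First, the enrolled number, the attrition rate and the evaluable number sit in one paragraph, and any two of them contradict the third. Second, the number to which every stated power is attached means after attrition in one section and before attrition in the other.

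The reader therefore cannot tell whether the trial meets its planned power exactly, exceeds it, or falls slightly short. The 398 patients to be randomized appear in no power statement. A single evaluable count also cannot serve both primary endpoints, because the plan expects 20% loss for step count and none for the CCI.

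**Working it through.** **Inputs.** Section 3.1: 398 enrolled (199 per group), 20% attrition, 332 evaluable (166 per group). Section 13.2: 332 with 80% power and one-sided alpha 0.025 (Aim 1); 332 with 88% power and critical p-value 0.024 (Aim 2); 12 evaluations per participant.

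**Step 1. Can 398 be reproduced from 332 and 20%?**

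- Evaluable divided by (1 − attrition): 332 / 0.80 = 415, which is 17 more than 398.
- Enrolled times (1 − attrition): 398 × 0.80 = 318.4, or 159.2 per group, which is 14 fewer than 332.
- Attrition implied by 398 and 332: 1 − 332/398 = 16.6%.
- Counting the 40 focus-group patients does not help: 438 × 0.80 = 350.4, and 1 − 332/438 = 24.2%.
- Multiplying instead of dividing gives 332 × 1.20 = 398.4 and 166 × 1.20 = 199.2, which match 398 and 199.

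The last line suggests that 332 was multiplied by 1.2 rather than divided by 0.8. It does not prove it, and the documents do not show which figure is wrong.

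**Step 2. What does 332 mean in Section 13.2?** For Aim 1, taking 20% from an initial 332 leaves 332 × 0.80 = 265.6, about 266. The encounter estimate is 332 × 12 = 3,984, the stated 4,000 or so, so it takes 332 as the whole sample.

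**Step 3. Effect on power.** The slope SD and correlation (Aim 1) and the CCI event rates (Aim 2) are not given, so the stated powers cannot be recomputed from first principles. They can be rescaled, because the expected test statistic grows with the square root of the sample size:

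power(n) = Φ[(z_alpha + z_power) × √(n/332) − z_alpha]

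Aim 1 uses z_alpha = 1.960 and z_power = 0.842. Aim 2 uses z_alpha = z(0.976) and z_power = z(0.88). At n = 332 the formula returns the stated 80% and 88%. If 332 was a starting number, it is compared with 398 randomized, since the same 20% applies to both and cancels. If it was an evaluable number, it is compared with 318.

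| Planned surgery not done (on top of the 20%) | Aim 1, 332 = starting number | Aim 1, 332 = evaluable number | Aim 2, no loss to follow-up |
|---|---|---|---|
| None | 86.6% (n = 398) | 78.3% (n = 318) | 93.0% (n = 398) |
| 5% (assumed) | 84.8% (n = 378) | 76.2% (n = 302) | 91.7% (n = 378) |
| 10% (assumed) | 82.9% (n = 358) | 74.0% (n = 287) | 90.3% (n = 358) |

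The counts are 398 × 0.95 = 378.1, 398 × 0.90 = 358.2, 378.1 × 0.80 = 302.5 and 358.2 × 0.80 = 286.6. The 5% and 10% are illustrations, because the plan gives no such rate. Using 0.975 in place of 0.976 for Aim 2 changes its results by less than 0.1 point. Aim 3 cannot be rescaled, since no effect size or alpha is stated.

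**The case against.** The strongest defence is timing. Section 3.1 attaches no time point to the 20% but places the 332 at Day 30, and follow-up runs to Day 90. Attrition of 16.6% by Day 30 and 20% by Day 90 would make the figures compatible. Nothing in the documents says this, and Section 13.2 puts a full 20% loss of accelerometer use by Day 14, so the defence fails.

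A second objection is that not all of Section 13.2 shows 332 to be a starting number. This is partly right. With no loss expected in Aim 2, starting and evaluable counts coincide, and the encounter estimate could describe either. The conflict rests mainly on the explicit Aim 1 wording, supported by Aim 3. That is enough, since Aim 1 is a primary comparison.

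Third, the harm is small. This stands. On the Section 13.2 wording the trial has more power than stated. On the Section 3.1 wording Aim 1 loses under 2 points. If Section 3.1 were taken literally for both primary endpoints, Aim 2 at 318 would have about 86.6% instead of 88%, but Section 13.2 expects no CCI loss.

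Fourth, enrolling 415 would also repair the arithmetic. That is true, but it adds 17 patients to recover about 2 points on only one of the two readings.

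Finally, the surgery-loss scenarios are assumptions. They are prompted by the ITT definition, and the main finding does not depend on them.

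**Conclusion.** The concern holds. The figures 398, 20% and 332 are incompatible by 14 evaluable patients (if 398 and 20% stand) or 17 enrolled patients (if 332 and 20% stand). That is about 4% either way, too much for rounding. Separately, 332 has two meanings. Neither finding needs any input that the plan leaves out.

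The consequence for power depends on what 332 meant. As a starting number, the stated powers are conservative for 398: about 87% for Aim 1 and 93% for Aim 2. As an evaluable number, Aim 1 is at about 78% rather than 80%, and at 76% or 74% if an assumed 5% or 10% without the planned surgery comes on top of the 20%. An underpowered trial is not shown.

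The power figures are approximate. They rescale the planning tests, not the joint model or the adjusted logistic regression. They also treat Aim 2 as a single test at 0.024, although the reference to cumulative alpha may mean a sequential design.

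**What to change.** Keep enrolment at 398, and keep the 20%, which Section 3.1 bases on pilot and earlier studies. Do not lower it to 16.6% to make 332 come out. Then:

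1. Confirm from the original power runs whether 332 was the starting or the evaluable number. Use it with that one meaning, or remove it, in Sections 3.1 and 13.2.
2. State whether the 20% includes patients who do not have the planned surgery, and give the assumed percentage.
3. Replace the single evaluable count in Section 3.1 with one per endpoint. For Aim 1 step count this is about 318 (159 per group) if the 20% includes that loss, and fewer if not (about 302 at 5%, 287 at 10%). For the Aim 2 CCI it is 398 less patients without the planned surgery (about 378 at 5%, 358 at 10%).
4. Restate power for Aims 1, 2 and 3 from 398 randomized, and report the inputs: slope SD and correlation, CCI event rates, and the Aim 3 effect size and alpha. If 332 meant evaluable, report the lower Aim 1 power as it is.
5. Recompute the encounter estimate from the sample finally stated.

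The cost is wording in the protocol and SAP, three power reruns (Aims 1 and 2 in East, Aim 3 in SAS PROC POWER) and one assumed percentage that the sponsor must supply. Enrolment, endpoints and analyses stay as they are. The possible price is a less favourable Aim 1 figure: about 78%, or lower if surgery loss comes on top of the 20%.

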3.1.1 Disease Status

We are targeting patients across all stages of disease.

3.1.2 Age Criteria, Performance Status and Life Expectancy

Age criterion for this trial is based on the NIH's age criteria, which defines an adult as individuals 18 years and over. There are no restrictions related to performance status or life expectancy.

3.1.3 Child Bearing Potential

Not applicable.

3.1.4 Protocol-Specific Criteria

Not applicable.

3.1.5 Informed Consent/Accent

All subjects must have the ability to understand and the willingness to sign a written or electronic informed consent.

3.1.6 Prior Therapy

Not applicable.

3.2 Exclusion Criteria

3.2.1 Study-Specific Exclusions

Not applicable.

3.2.2 Non-Compliance

Subjects, who in the opinion of the investigator, may not be able to comply with the safety monitoring requirements of the study.

3.3 Inclusion of Women and Minorities

The study is open to anyone regardless of gender or ethnicity. Efforts will be made to extend the accrual to a representative population.

4.0 Screening and Registration Procedures

4.1 Screening Procedures

All eligible patients who meet study inclusion criteria will be identified through the Department of Surgery and all solid tumor surgery outpatient clinics at all participating sites. Research Nurses and CRAs will work with surgeons to identify eligible patients. Surgeons will notify the research staff, and staff will contact eligible patients to explain the study purpose, answer any questions, and ascertain interest in participation. Research staff will also attend key clinics and meetings (ambulatory clinics, tumor boards) on a weekly basis to identify eligible participants. If the patient agrees to participate, informed consent will be obtained in person or via mail, electronic mail, or other electronic applications (i.e. DocuSign) to obtain electronic signatures from each patient per standard practice.

. The Research Nurses and CRAs will be responsible for obtaining informed consent and study implementation.

4.2 Informed Consent

The investigational nature and objectives of the trial, the procedures and treatments involved and their attendant risks and discomforts, and potential alternative therapies will be carefully explained to the subject and a signed informed consent will be obtained in person or via mail, electronic mail, or other electronic applications (i.e. DocuSign) to obtain electronic signatures from each patient per standard practice. Research Nurses and CRAs will be bilingual (English and Spanish), to ensure that informed consent is conducted in a linguistically-appropriate fashion. If necessary (i.e. if potentials have left the clinic), a telephone/verbal informed consent will be obtained first in order to begin study in a timely manner. Signed informed consent will then be obtained for this study when participants are at COH, or emailed or mailed to them, or other elect and returned to COH when signed, or completed via other electronic applications (i.e. DocuSign). Documentation of informed consent will be maintained in the subject's research chart and electronic health records.

We will obtain the following information from the EHR to track characteristics of patients who are screened as eligible but declined participation. Age, gender, race/ethnicity data will be obtained from the EHR on patients that declined participation. No other PHIs will be collected for patients who declined participation. In addition, if declined patients are willing, reasons for decline will be obtained verbally.

We will track and report ethnic minority retention weekly during standing research team meetings and reports. Reports will be generated weekly to show data on ethnic minority retention. Efforts will be made to improve retention if retention is low and/or problematic.

4.3 Registration Requirements/Process

The Research Nurses and CRAs will establish eligibility and consent before contacting the registrar at the time of enrollment. The registrar will enter the patient on a pre-established randomization log, and report the assignment to the Research Nurses and CRAs, who will then communicate the assignments to the participants in both study arms. Participants will complete baseline assessment following informed consent.

4.4 Randomization and/or Dose Level Assignment

Each patient will be randomly assigned to either the remote perioperative telemonitoring or surgeon only perioperative care arm, using a stratified and blocked randomization. Strata will be defined by diagnosis (GI, GU, GYN) and surgical technique (minimally-invasive versus open). Variable block sizes will be used to maintain approximate balance and pre-assignment masking.

[figure not shown]

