Comparative Effectiveness Trial of Perioperative Telemonitoring for Functional Recovery and Symptoms
Brief Protocol Title for the Lay Public (if applicable):
NA
Study Phase:
Phase III Interventional
Participating Sites:
COH Duarte, COH South Pasadena, COH Antelope Valley, and COH Upland.
Rationale for this Study:
Patients experience a decrease in functional capacity following their surgery with an increase in symptoms, resulting in a dramatic decline in their quality of life (QOL). In addition to these challenges, patient's postoperative care and recovery primarily takes place in home settings due to increasing pressures to reduce readmissions and earlier postoperative discharge by the health care systems. As a result, physical function can decline severely and symptoms can progress before the surgical team is notified.
Objectives:
The primary purpose of this study is to test the efficacy of remote perioperative telemonitoring for functional recovery and postoperative complications in 438 GI, GU, GYN cancer surgery patients (398 patients for main trial, 40 for focus groups), comparing remote perioperative telemonitoring and surgeon care only patients.
Study Design:
This is a prospective, randomized, mixed methods, comparative effectiveness trial (1:1 randomization) of perioperative telemonitoring in cancer surgery (GI, GU, GYN). We plan to enroll 438 subjects (398 patients for the main trial, 40 for focus groups) over an approximate 40 months. This study will utilize the TapCloud™ application to conduct study procedures. Patients enrolled in the study will use the TapCloud™ application to capture subjective ePROs (symptoms). Patients will also be given an Actigraph GT9X Link, a research-grade accelerometer, to capture and report functional activity data (daily steps and sedentary time) throughout the duration of the study to the TapCloud™ application. The remote perioperative telemonitoring program consists of a real-time, alert/feedback system that will trigger alerts into the TapCloud™ application when pre-determined thresholds are exceeded. Clinical RNs will respond by initiating contact using the TapCloud™ application's secure messaging system, or telephone calls if unsuccessful, to assess, triage, manage, and resolve the issue.
Endpoints:
Primary:

Higher daily steps, lower postop complications Secondary: Sleep, sedentary time, symptom severity, symptom interference, readmissions
Sample Size:

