1.0 Goals and Objectives (Scientific Aims)

The most common and effective treatment for cancer is surgery. By definition, surgical procedures are invasive; patients experience an abrupt decline in functional capacity after surgery. In addition to postoperative functional declines, patients experience an increase in symptoms, such as pain, fatigue, and distress.¹⁻³ Postoperatively, these symptoms contribute to a dramatic decline in quality of life (QOL).⁴⁻⁶ Postoperative recovery challenges are compounded by healthcare systems-related trends, including pressures to reduce readmissions and earlier postoperative discharge. As a result, the majority of postoperative care and recovery takes place at home. After hospital discharge, physical function can decline severely and symptoms can progress before the surgical team is notified.

A promising approach to early identification of post-discharge complications is through remote, real-time perioperative telemonitoring of functional activity and patient-reported outcomes (PROs). The approach can identify patients at risk for post-discharge complications, treat symptoms/complications in a real-time fashion, and prevent readmissions. The overall purpose of this study is to conduct a multi-site, comparative effectiveness, randomized controlled trial of perioperative telemonitoring for functional recovery in 438 English and Spanish-speaking cancer patients (398 for the main trial, 40 for the focus groups) scheduled to undergo major abdominal surgery (GI, GU, GYN). The program will be implemented at three geographically diverse sites in the Greater Los Angeles area, including one serving a low resource, socioeconomically-disadvantaged population. Accordingly, we propose the following specific aims:

Aim 1: Compare the impact of remote perioperative telemonitoring care versus surgeon only perioperative care on clinically significant changes in functional recovery (accelerometer daily step count) and related secondary patient-centered outcomes (sleep, sedentary time, symptom severity, symptom interference with daily activities).

Hypothesis: Remote perioperative telemonitoring improves functional recovery after major abdominal surgery.

Aim 2: Compare the impact of remote perioperative telemonitoring care versus surgeon only perioperative care on postoperative complications (Comprehensive Complications Index – CCI) and related secondary surgical outcomes (hospital readmission).

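### Enrolment site is in neither the randomisation strata nor any planned model; prespecifying it would be a small, nearly free gain in precision

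*Combined protocol and SAP*

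**What the plan says.** **Randomisation (Section 4.4).** "Strata will be defined by diagnosis (GI, GU, GYN) and surgical technique (minimally-invasive versus open". That makes 3 × 2 = 6 strata, and site is not one of the factors.

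**Covariates (Section 13.2).** There are two lists. Under Internal/External Validity, the hypothesis tests are to be "adjusted for covariates (age, sex, physical fitness at pre-surgical baseline". The other list, in the paragraph on methods for each aim, reads: "Characteristics considered as potential covariates in all analyses will be age, sex, surgical technique, residential setting, and physical fitness at preoperative baseline". A candidate that betters the "fit to the observed data will be retained in the final analysis". Neither list has site.

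**Route for further variables (Section 13.2, Preliminary Analysis).** "Significant relationships/correlations will guide the addition of demographic variables to the analysis". Site is not a demographic variable.

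**Models (Section 13.2, Aims 1 and 2).** The Aim 1 step sub-model has treatment and covariates as fixed factors and patient as the only random factor. The Aim 2 model is a logistic regression of maximum CCI split at 15. Neither names a site term.

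**Sites.** Section 1.0 speaks of three geographically diverse sites, "including one serving a low resource, socioeconomically-disadvantaged population". The synopsis lists "COH Duarte, COH South Pasadena, COH Antelope Valley, and COH Upland", Section 3.1 refers to minority accrual "at all four participating sites", and Section 14.4 says three and then names four.

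**The concern.** The protocol itself gives some reason to expect outcomes to vary by site. The catchments differ. The conceptual framework in Section 5.1 treats access to care as an influence on symptoms and, through them, on activity. Prehabilitation referral in the comparator arm is left to the surgical team, and the first postoperative visit may fall anywhere from 1 to 4 weeks after discharge.

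If site is prognostic, two things follow. The arms can differ by chance in site mix, because site is not a stratum, and the models as written would not correct for that. Some precision is also given up on the primary endpoints. The choice has to be made in advance: adding site after unblinding would be a post hoc decision in a plan that already selects covariates by fit.

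**Working it through.** **1. Textual check.** Site was looked for in each place where it could enter: strata (Section 4.4), both covariate lists, the demographic route, the Aim 1 fixed and random terms, and the Aim 2 model (Section 13.2). It is in none of them. The figure under Section 4.4 is not shown in the text available, so its content could not be checked. Residential setting is the nearest listed proxy. It describes the patient's home, is not defined, and stays only if it improves fit.

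**2. The plan's own power figures.** Neither can be reproduced. Aim 1 (80%, 14% slope difference, 1-sided 0.025, n = 332) gives no SD or within-patient correlation. Aim 2 (88%, 1-sided 0.024) gives no control rate or effect size. Back-solving instead:

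- Aim 1, treating 14 as a difference in means in percentage points: SD = 14 / [(1.960 + 0.842) × √(2/166)] = 45.5 with 166 per arm, or 40.7 with 133 per arm after 20% attrition.
- Aim 2, unpooled two-proportion formula with 166 per arm: 88% corresponds, for example, to 30% vs 15.7% or 40% vs 24.1%.

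**3. Linear approximation.** The stated power fixes δ = z(1−α) + z(power). That is 1.960 + 0.842 = 2.802 for Aim 1 and 1.977 + 1.175 = 3.152 for Aim 2. If site carries a share ρ of outcome variance (assumed; not in the documents), adjusted power = Φ(δ/√(1−ρ) − z(1−α)). Example for Aim 1 with ρ = 0.05: 2.802/√0.95 = 2.874; 2.874 − 1.960 = 0.914; power 82.0%.

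| ρ (assumed) | Aim 1, from 80% | Aim 2, from 88% |
|---|---|---|
| 0.01 | 80.4% | 88.3% |
| 0.02 | 80.8% | 88.6% |
| 0.05 | 82.0% | 89.6% |
| 0.10 | 84.0% | 91.1% |

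The Aim 2 column borrows a linear-model formula and is only indicative.

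**4. Simulation by type of test.** N = 332, 1:1, not stratified by site, assumed site shares 60/15/15/10%. For the slope test, adjusting means letting the slope differ by site.

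| Test | Assumed site effect | Power ignoring site | Power adjusting |
|---|---|---|---|
| Aim 1, mean difference | none | 0.796 | 0.792 |
| | ρ = 0.05 | 0.804 | 0.821 |
| | ρ = 0.10 | 0.800 | 0.834 |
| Aim 1, slope difference | constant over time, site SD = patient SD | 0.798 | 0.796 |
| | 5% of slope variance | 0.784 | 0.801 |
| | 9% of slope variance | 0.755 | 0.792 |
| Aim 2, logistic, 30% vs 15% | none | 0.901 | 0.899 |
| | site log-odds SD 0.3 | 0.897 | 0.903 |
| | site log-odds SD 0.6 | 0.842 | 0.869 |

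Differences of half a point or so are within simulation error. With site ignored and no treatment effect, 1-sided rejection rates were 0.024 to 0.026 (mean difference, nominal 0.025), 0.021 to 0.028 (slope, nominal 0.025) and 0.018 to 0.021 (logistic, nominal 0.024). Omitting site does not inflate type I error.

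**5. Chance imbalance.** For a site with a quarter of the patients (assumed), the SD of the between-arm difference in its share is √(0.25 × 0.75 × 2/166) = 0.0475, or 4.8 points. With an assumed 20-point site gap in percent change, the typical shift in the treatment estimate is 20 × 0.0475 ≈ 1 point. The back-solved standard error is 45.5 × √(2/166) ≈ 5 points, so the shift is about 0.2 standard errors. With the 60/15/15/10% shares, the largest between-arm difference in any site's share averages 5.8 points (95th percentile 10.8).

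**The case against.** The case for leaving the plan alone is respectable. Analysis without site is valid under this randomisation, and since site is not a stratum, no design factor has to be carried into the model. Site differences are conjecture: all four locations belong to one institution, Section 5.1 describes a single comparator pathway with referral varying by surgeon, Section 35-style uniformity is sought through the nurse training described in Section 5.1, and the documents do not say that surgery takes place where the patient enrolled. Chance imbalance is already reflected in the standard error. All of this stands, and it is why the point is small. It does not give a reason to prefer omission, since adjusting costs almost nothing when site carries no information (0.796 vs 0.792; 0.901 vs 0.899).

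A reader might also infer more than the documents support:

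- *That the covariate list is closed, so site could never be adjusted for.* Section 13.2 gives two differing lists and lets demographic variables be added. The accurate statement is that no listed route reaches site.
- *That all site differences stay in the error term of both primary analyses.* For Aim 1, percent change from the patient's own baseline removes differences that scale with baseline steps, and on the slope test the patient effect absorbs differences constant over time. Aim 2 is logistic and has no additive error term; there, omission attenuates the conditional odds ratio and loses some power.
- *That sites were chosen to differ, or that site diversity is the trial's rationale.* Section 1.0 only describes them as geographically diverse. The rationale in the synopsis is functional decline, symptoms and recovery at home.

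**Conclusion.** The point holds as a modest, nearly free improvement, not as a validity failure. Site appears nowhere in the strata, covariate lists or primary models, so any prognostic site differences go unadjusted.

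The size is about 0 to 4 power points. It rests on assumed site variance shares of 1% to 10%, assumed site log-odds SDs up to 0.6 and assumed site shares; none of these is in the documents. The benefit is clearest for Aim 2. For Aim 1 it depends on which contrast is tested, and Section 13.2 leaves this open: power is computed for a difference of slopes, while the model description names treatment but no treatment-by-time term. If the main effect of treatment is tested, constant site differences in percent change cost precision. If the slope difference is tested, only site-by-time differences do, and a plain site term would recover nothing.

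**What to change.** Amend Section 13.2 before any unblinded analysis:

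1. Include enrolment site as a fixed covariate in the Aim 1 step sub-model and the Aim 2 logistic model, exempt from the rule that keeps covariates according to fit.
2. State whether the Aim 1 test is the treatment main effect or the slope difference. If it is the slope difference, add a site-by-time term.
3. Give a numeric minimum number of patients per site, and name in advance how a site below it is pooled.
4. Reconcile the site count: three in Sections 1.0 and 14.4, but four in Section 3.1 and four named in the synopsis and Sections 14.2 and 14.4.

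The cost is a few sentences in the SAP and at most 3 degrees of freedom for four sites, plus up to 3 more for a site-by-time term with time entered linearly. No new patients are needed, and enrolment site is known for every patient.
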